APPENDIX E: PHYSICIAN PREFERENCE FOR TREATMENT ASSIGNMENT SURVEY

We are conducting a study to better understand whether patients and their doctors are comfortable letting a “coin flip” decide whether lower- or higher-intensity chemotherapy is used. We would like to ask you two questions about your preference for treatment assignment and which factors are important for making this decision. It should take about 5 minutes. There are no foreseeable risks to your participation. There is no payment for taking part in this research and your participation is voluntary. Choosing not to participate will not incur a loss of benefits to which you are otherwise entitled. You will not directly benefit from taking this survey, but we hope we can better understand how decisions about treatment intensity are made. We will ask you to provide your name and we will link your responses to similar questions we are also asking the patient you are treating. However, your name will remain confidential and if results of this study are published we will not use your name. If you have questions about this study, please contact [name] MD at [contact]. If you have questions about your rights as a research participant, you can contact [name], Director of the Institutional Review Office, Fred Hutchinson Cancer Research Center, at [contact].

1) Preference for treatment assignment

After thinking about this study and discussing it with the patient, how do you prefer for the patient to be treated.

- I am willing to randomize the patient to lower- or higher intensity chemotherapy and they agree
- I am willing to randomize the patient to lower- or higher intensity chemotherapy but the patient would prefer to choose treatment themselves and they chose:
 - Lower-intensity chemotherapy
 - Higher-intensity chemotherapy
- Neither I nor the patient want to proceed with randomization and the following person chose the treatment arm:
 - Myself
 - The patient

2) Which factors were most important for you in making this decision?

- The patient did not want to be randomized (did not like the idea of a “coin flip”)
- The patient thought one treatment arm was better than another
- I thought one treatment arm was better than another

- I thought the patient was too frail/unfit for the higher intensity treatment and that this arm would be too toxic
- I was concerned the lower intensity arm would not be efficacious enough
- Other, please explain:

Physician name: _____

Date: _____

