The TRM score, computationally derived from the “simplified” TRM model, is now in routine use at Fred Hutch, where research protocols now primarily assign patients based on predicted likelihood of TRM (e.g. NCT01342887, NCT01567059, NCT01607645, NCT01729845, NCT01804101, NCT02044796, NCT02121418, NCT02728050). Because the early death rates following intensive chemotherapy in adults with AML have declined substantially over the last 2 decades,^{13,14} we very recently re-examined the value of the “simplified” TRM model to predict early deaths in patients treated at Fred Hutch.¹⁵ Among 285 patients with newly diagnosed AML treated with intensive induction chemotherapy from 2008-2014, 17 (6.0%) died within 28 days, with the AUC of the TRM score being 0.76,¹⁵ indicating the continued value of multicomponent modeling to predict early deaths after AML therapy. So far, the comparative abilities of a model such as the one that underlies the TRM score and “physician intuition” (“I know it when I see it”) to predict TRM are uncertain. Moreover, an AUC of 0.75-0.80 approximately intermediate between certainty (AUC=1.0) and a coin flip (AUC=0.5). Therefore, although the TRM score will be the principal eligibility criterion for the pilot randomized trial, an important part of this application will be examining (a) whether incorporation of other covariates (e.g. HCT-CI, ELN risk group) will improve the ability to forecast TRM and (b) the concordance between our models and simple physician judgment. While we have developed online means to rapidly compute TRM scores (<https://cstaging.fhcrc-research.org/TRM/Default.aspx>), it is perhaps naïve to expect widespread use barring a quantitative demonstration of the value of predictive models.

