2.2 Exploratory Objectives

- 2.2.1 To evaluate the attitude of patients and physicians toward randomization and explore reasons for treatment preference.
- 2.2.2 To evaluate whether the ability to assess fitness for intensive chemotherapy can be improved by an augmented treatment-related mortality (TRM) score that includes additional (co-morbidity) factors, and to compare the ability of physicians and the prediction algorithm(s) to assess the likelihood of early death.
- 2.2.3 To compare, within the limits of a pilot study, response, duration of response, and survival between patients receiving intensive and those receiving non-intensive chemotherapy.
- 2.2.4 To describe the impact of treatment intensity on quality of life of patients undergoing chemotherapy for newly diagnosed AML.
- 2.2.5 To describe the impact of treatment intensity on medical resource utilization and care cost of patients undergoing chemotherapy for newly diagnosed AML.

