14.3.2 Exploratory endpoints

This pilot study will use exploratory, descriptive, and observational methods to

- 1) Evaluate the attitude of patients and physicians toward randomization and explore reasons for treatment preference
- 2) Evaluate whether the ability to assess fitness for intensive chemotherapy can be improved by an augmented treatment-related mortality (TRM) score that includes additional (co-

morbidity) factors, and to compare the ability of physicians of the prediction algorithm(s) and physician to assess the likelihood of early death

3) Estimate differences between patients treated with lower-intensity G-CLAM and those treated with higher-intensity G-CLAM with regard to anti-leukemic efficacy (response, duration of response) and survival, QOL, and medical resource utilization as well as care cost

Importantly, this trial is not powered to detect statistically significant differences between the study arms for these clinically important endpoints. Rather, the primary goal is to estimate outcomes with both treatment intensities to inform a subsequent larger study, should follow-up investigation appear warranted.

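### No form or section records a physician's estimate of early death, so the physician-versus-algorithm comparison in objective 2.2.2 cannot be made for day-28 discrimination; a smaller gap is one missing answer in Appendix E question 1

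*Combined protocol and SAP*

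**What the plan says.** The aim appears three times in the combined protocol and SAP. Section 1.0 lists "the concordance between our models and simple physician judgment" among the matters to be examined and presents this work as important. Section 2.2.2 turns it into an exploratory objective: "to compare the ability of physicians and the prediction algorithm(s) to assess the likelihood of early death". Section 14.3.2 repeats it, with a slip in the wording: "to compare the ability of physicians of the prediction algorithm(s) and physician to assess the likelihood of early death".

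Two of the three ingredients are defined. The TRM score is required for entry (3.1.3, formula in Appendix A). Early mortality is death from any cause by day 28 after starting therapy (14.4).

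For the physician, section 8.2.4 describes a survey handed out at enrollment about agreement to randomization and the reasons for it. The form itself, Appendix E, announces: "We would like to ask you two questions about your preference for treatment assignment and which factors are important for making this decision". Its introduction says the answers will be linked to the patient's survey (Appendix D).

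**The concern.** A comparison of two predictors needs both predictions. If the physician's prediction is not written down before the outcome is known, it cannot be obtained later without hindsight. Every patient treated without the item is therefore lost to this part of the objective.

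Timing matters as well. Section 1.0 states that "the TRM score will be the principal eligibility criterion for the pilot randomized trial" and that the score "is now in routine use at Fred Hutch". A physician asked at enrollment may already know the score, and agreement could then reflect that knowledge rather than independent judgment.

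Separately, objective 2.2.1 concerns physicians' attitudes to randomization. If the patient is willing and the physician is not, none of the answers to question 1 fits.

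**Working it through.** **1. The plan's own figures.** The one design calculation, in 14.3.1, reproduces. The exact binomial probability of 26 or more of 50 is 0.902 at a true rate of 60% (stated 90%), 0.057 at 40% (stated 6%) and 0.0009 at 30% (stated below 1%). It counts patients' agreement only, so nothing below alters it.

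**2. Search for the physician's estimate.**

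| Place | What it collects | Physician estimate of early death? |
|---|---|---|
| 6.1 Baseline | History, marrow, blood counts, chemistry, LVEF | No |
| 8.2.1 | QLQ-C30 | No |
| 8.2.2, 8.2.3 | Complications, resources, cost | No |
| 8.2.4 | Patient and physician preference surveys | No |
| Appendix D | Patient's preference, how it was reached, factors | No |
| Appendix E | Physician's preference, factors | No |

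The contents list gives Appendix F as a fax cover sheet, so a further form is unlikely to be hidden there. Items specified: 0.

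**3. Nearest substitute.** Question 2 of Appendix E has a box for a patient judged too frail or unfit for the higher-intensity arm. It is one possible reason for a decision. It carries no risk level and no time horizon, and it does not address the lower-intensity arm. A blank box is not a prediction of survival, and non-return of the survey is not a deviation (8.2.4).

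**4. Question 1 of Appendix E.**

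| | Patient willing | Patient not willing |
|---|---|---|
| Physician willing | Option 1 | Option 2 |
| Physician not willing | none | Option 3 |

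Three of four combinations are covered.

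**5. What the added item could deliver.** Expected early deaths among 50 patients:
- Appendix A, score band 13.11 to 22.8 (20%): 50 × 0.20 = 10
- CPX-351 trial in 14.4 (27%): 50 × 0.27 = 13.5, about 14
- Appendix A, above 13.1 (31%): 50 × 0.31 = 15.5, about 16

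The paired difference in AUC was simulated from a binormal model. Assumptions: equal true AUCs of 0.62 or 0.70, and a physician-score correlation of 0.3 or 0.7. The half-width is 1.96 × SD of the difference.

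| Deaths of 50 | 95% half-width |
|---|---|
| 10 | 0.149 to 0.233 |
| 14 | 0.133 to 0.209 |
| 16 | 0.128 to 0.201 |

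Concordance needs no deaths. For an assumed rank correlation of 0.5 with 50 pairs, Fisher's z is 0.549 and its SE is √((1 + 0.5²/2)/47) = 0.155. The 95% CI is 0.24 to 0.69.

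**6. Why prior knowledge of the score should be recorded.** Suppose the reported estimate is (1−w) × own view + w × score, both standardised, and the own view correlates r₀ = 0.30 with the score. The observed correlation is ((1−w)r₀ + w)/√((1−w)² + w² + 2w(1−w)r₀). At w = 0.25 this is 0.475/√0.7375 = 0.55; at w = 0.50 it is 0.65/√0.65 = 0.81. The weights and r₀ are assumptions chosen for illustration.

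**The case against.** The strongest reply is that physician judgment need not be a number. Section 1.0 speaks of concordance, and it reads physician judgment in the AZA-001 trial from the regimen investigators selected before randomization. Appendix E records willingness and the frailty reason, and the arm received is known. This stands in part: a coarse concordance analysis is possible. A reader might infer that no physician comparison at all can be made; the documents do not support that. What cannot be made is a comparison of discrimination for day-28 death.

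A reader might also take the statement in 13.0 that no case report forms are used as proof that the item is absent. It adds little, because the same section describes a database filled from charts and other source documents. HCT-CI, named in 1.0 for the augmented score, is not listed in 6.1 or 8.2 either. The difference is that HCT-CI could be abstracted from the record later and a prediction could not.

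On question 1, section 8.2.4 stresses the physician who agrees when the patient does not, which is option 2. The missing pattern can often be inferred from question 2 and the linked Appendix D. That makes the gap minor. It remains a gap because either survey may not be returned.

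Finally, the objective is exploratory, and 14.3.2 says the trial is not powered for differences between arms. That limits the consequence but does not supply the missing variable.

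**Conclusion.** The concern holds in this form: objective 2.2.2 and section 14.3.2 promise a comparison for which no physician estimate is specified. Discrimination for day-28 death cannot be compared from the planned data, and only a crude concordance reading is available. The missing question 1 option is a separate, minor defect. The effect is confined to objectives 2.2.1 and 2.2.2. The augmented-TRM half of 2.2.2 does not depend on a physician estimate, and the 26-of-50 rule is unchanged.

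The half-width of about 0.13 to 0.23 rests on the assumed AUCs and correlations, on full return of the form, and on early-death rates of 20% to 31%.

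Two stronger readings should be resisted:
- A reader might expect far fewer deaths, since section 1.0 says "Because the early death rates following intensive chemotherapy in adults with AML have declined substantially over the last 2 decades" and reports that "17 (6.0%) died within 28 days" among 285 patients at the centre. Those were intensively treated patients not selected for a high score. The 27% comes from an ongoing trial with essentially the same entry criteria, so scaling it down for historical decline is not justified. Setting the centre's figure against the older derivation cohort also mixes centres and eras.
- A reader might use the Appendix A bands to put a figure on the discrimination lost through entry at 13.1 or above. Only two bands remain above the cut, and ties within them exaggerate the loss. The documents support the direction (a restricted range) but not a size.

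**What to change.** In Appendix E:
- Add one item: the physician's estimated probability (0 to 100%) that the patient dies within 28 days of starting (a) lower-intensity and (b) higher-intensity chemotherapy, completed before the assignment is known.
- Add a tick-box for whether the TRM score was already known.
- Correct the number of questions stated in the introduction.
- Add to question 1: *The patient is willing to be randomized but I am not.*

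In 14.3.2, state a descriptive analysis:
- Rank correlation of the higher-intensity estimate with the TRM score, which was developed in intensively treated patients.
- AUCs of the physician's estimate and of the score for day-28 death, with 95% CIs.
- A note that entry at a score of 13.1 or above restricts the score's range, and that knowing the score may inflate agreement.

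If the item is not added, delete the physician comparison from 2.2.2 and 14.3.2. Leave the 26-of-50 rule as it is.

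The cost is a minor amendment and about a minute of physician time per patient. The result will be imprecise and possibly anchored to the score, so it can inform a later study but not settle the question.
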